9.2.2 Visit 2 (Week 0, baseline)

At Visit 2 eligibility must be re-assessed before the patient is randomized to a treatment arm. Please note: laboratory eligibility criteria are based upon local and historical records, not central laboratory findings. Even retrospectively, central laboratory results from the baseline visit will not render a patient ineligible for the study. If a patient is not eligible for randomization, or withdraws for other reasons before randomization, he / she will be considered a screening failure even though the visit is not named a screening visit (for details see Section 6.4.1).

The following procedures will be performed **before randomization**:

- Review in/exclusion criteria and confirm patient eligibility
- Quality of life questionnaires (KCCQ and EQ-5D-5L), to be completed by the patient (Section 9.4.4)
- Medical and surgical history collection and recording (Section 9.3.2)
- Tobacco smoking and alcohol history collection and recording
- Assessment of caffeine-containing beverage and chocolate consumption during the previous 4 weeks
- Physical examination (Section 9.6.3.2)
- Weight and height measurement (BMI will be calculated automatically)
- 12-lead ECG (Section 9.6.3.3)
- NYHA class assessment (Section 9.4.3.2)
- Blood pressure and heart rate measurement (Section 9.6.3.4)
- Adverse events assessment (Section 9.6.1.3)
- Concomitant medication collection and recording (Section 8.1)
- Collection of AVIVO device applied at Visit 1 (Week -1)
- Echocardiography (Section 9.4.1)

- AVIVO device application, worn for 7 days (Section 9.6.3.5)

After all above procedures are done, the patient can be randomized via IxRS (Section 7.3).

The following procedures should be performed **after randomization and before study medication intake**:

- Blood sampling for safety (Section 9.6.3.1)
- Blood and urine sampling for biomarkers (Section 9.4.2)
- Study drug dispensing (Section 7.7)

The following procedures should be performed **during and after study medication intake**:

- Start of study medication (Section 7.1). The first dose of study medication will be taken after all previous procedures are completed; the time of intake should be recorded. The patients will be instructed to remember the time of medication intake as precisely as possible on selected days.

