4.3 Handling of Missing Data

All missing or partial data will be presented in the patient data listing as they are recorded in the eCRF.

A number of descriptive analyses will be performed to better understand missing data patterns. The frequency, proportion and the reasons for premature discontinuation of both the study and study treatment will be reported. Kaplan-Meier plots for “time to end of study treatment (calculated as days from first dose to the earliest date of stop medication, including premature stop of study medication and death, for the calculation all the subjects will be considered to have an event-stop of study medication)” and “time to end of study”(calculated from randomization to the earliest date of visit 9, death, and the last visit if subject drops off from study prematurely, for the calculation all the subjects will be considered to have an event-stop of study) will be provided, by treatment group and overall.

The number of patients who prematurely discontinue study participation or intake of study medication will be summarized with respect to the key subgroups, see section 6.4.1. and the reasons for premature discontinuation of study and / or study treatment. If the proportion of patients who withdraw across the dose groups is not fairly balanced, the impact on the primary variables will be further explored. To further explore the missingness pattern with regards to the “missing at random” assumption, the mean of the baseline values of the efficacy variable will be summarized for patients with and without post-baseline observations, by treatment group and overall.

For the analysis of the primary and secondary variables, it cannot necessarily be assumed that data are missing at random. As the choice of primary analysis will be based on assumptions that cannot be verified, the robustness of the results of the primary analysis will be investigated through appropriate sensitivity analyses making different assumptions, in accordance with the EMA “Guideline on missing data in confirmatory clinical trials”. Detail missing data handling are specified in Section 6.2.1.4.

When appropriate, the following rules will be implemented so as not to exclude subjects from statistical analyses due to missing or incomplete data:

- **Date of CHF diagnosis**
For cases where start month and year are reported but day is missing, impute it with the 1st day of month. If the month is not available, this date will not be imputed.
- **Clinical outcomes**

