For cases where start month and year are reported but day is missing, impute the maximum of (date of randomization, first date of study medication, 15.month.year).
For cases where only start year is reported or completely missing, impute the maximum of (date of randomization, first date of study medication, 15.01.year), but not later than death date if the subject died.
- **Heart failure related concomitant medication start date**
For case where start month and year are reported but day is missing, impute it with 15th day of month. For cases where only start year is reported or completely missing, impute it as maximum of (15.01.year, randomization).
- **Heart failure related concomitant medication stop date**

For case where stop month and year are reported but day is missing, impute it as minimum of [(15, month, year) and (last visit date) and (death date)].

If the stop day and month are missing, then the stop date will be imputed as minimum of [(15.12.year) and (last visit date) and (death date)].

If the date is completely missing then the stop date will be imputed as minimum of [the last visit date and death date]. If the concomitant medication is “Ongoing at subject's last visit”, for the respective stop date variable the ‘last visit date’ from the corresponding domain is merged in the concomitant medication database by data management programming.

- **Study medication start date for subjects took study medication**

If the start date and time is missing it will be imputed with the randomization date and time. If start date and time is recorded as earlier than randomization and cannot be clarified, date and time of randomization will be used for the statistical analysis.

- **Study medication stop date for subjects took study medication**

If the stop day is missing, but the stop month and stop year are available then the stop date will be imputed as minimum of [(15, month, year) and (last on treatment visit date before the observational visit) and (death date)].

If the stop day and month are missing or the date is completely missing then the stop date will be imputed as minimum of [the last on treatment visit date before the observational visit and death date].

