4.5.1 Baseline and Change from Baseline

For efficacy endpoints, the efficacy baseline is defined as the last available value prior to or on the date of randomization. Safety baseline is defined as the last available value before the first study medication administration. If values are missing at the baseline (visit 2, week 0), data recorded at run-in (Visit 1) will be considered as safety baseline value. If run-in record is also missing, the baseline value will be left as missing.

Change from baseline for vital signs or laboratory parameters will in general be displayed as the difference to baseline defined as:

$$\text{Change} = \text{Post baseline value} - \text{baseline value.}$$

In addition, for some parameters the relative change will be analyzed defined as

$$\text{Relative change} = 100\% * [(\text{post baseline value} - \text{baseline value}) / \text{baseline value}].$$

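### Imputing the first-dose time as the randomization time can turn a valid pre-dose safety laboratory sample into a post-dose one

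*SAP*

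**What the plan says.** SAP 4.3 gives two rules for the start of study medication in patients who took it. The first covers an absent record: "If the start date and time is missing it will be imputed with the randomization date and time". The second covers an implausible one: "If start date and time is recorded as earlier than randomization and cannot be clarified, date and time of randomization will be used". Both belong to a list of rules to be used where appropriate, with the stated aim "so as not to exclude subjects from statistical analyses due to missing or incomplete data".

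Protocol 9.2.2 fixes the order of work at Visit 2. The safety blood belongs to the block done "after randomization and before study medication intake", and dosing closes the sequence: "The first dose of study medication will be taken after all previous procedures are completed; the time of intake should be recorded". Table 9–1 marks the Week 0 safety sample as pre-dose. Neither that table nor the Visit 1 list in Protocol 9.2.1 contains a blood sample at run-in.

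SAP 4.5.1 sets the baseline: "Safety baseline is defined as the last available value before the first study medication administration". If the Visit 2 value is missing, the Visit 1 value is used; after that, "If run-in record is also missing, the baseline value will be left as missing". The efficacy baseline in the same section is defined by date and includes the day of randomization.

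**The concern.** The imputed first-dose time is the earliest time that is compatible with randomization. By design, though, the safety sample lies between randomization and dosing. Moving the dose back to randomization therefore moves it past the sample that is meant to precede it.

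Two things are at stake for each patient to whom the rule applies. First, SAP 6.3.5 plans changes from baseline for every continuous laboratory parameter and names eGFR, bilirubin, AST and ALT. Without a baseline these changes cannot be calculated. Second, SAP 4.5 assigns each date to a phase relative to study treatment, and SAP 4.5.2 lets the any-time-post-baseline display take every measurement made after drug was started. An abnormal value drawn before dosing could therefore appear there and among the treatment-emergent out-of-range values.

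**Working it through.** The plan states no figure on this point, so the check is one of ordering, followed by simple arithmetic on size.

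**Inputs.** R = randomization time; L = time of the Visit 2 safety blood; D = true first-dose time; D* = first-dose time used in the analysis. Protocol 9.2.2 gives R < L < D. SAP 4.3 gives D* = R when the record is missing, or is earlier than R and cannot be clarified. SAP 4.5.1 accepts L as safety baseline only if L < D*.

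| First-dose record | Order without SAP 4.3 | Order after SAP 4.3 | L before first dose? |
|---|---|---|---|
| Recorded as planned | R < L < D | unchanged | yes |
| Missing | R < L, D unknown (truly later than L) | D* = R < L | no |
| Recorded before R, not clarified | recorded D < R < L | D* = R < L | no, with or without the rule |

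In the second row the rule creates the error, because the sample truly preceded the dose. In the third row the sample already appeared to be post-dose. The rule moves the dose closer to the sample but not past it, so it fails to repair the error.

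**Fallback.** Once L is rejected, SAP 4.5.1 turns to Visit 1. No blood is scheduled there, so the laboratory baseline is left missing.

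**What is not affected.** Protocol 9.2.2 places blood pressure, heart rate, weight and the 12-lead ECG before randomization, so these precede D* = R and keep their baselines. LVEF and NT-proBNP use the date-based efficacy baseline, which includes the day of randomization. Both primary variables are therefore untouched.

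**Does the result depend on how times are compared?** There are three possible readings of SAP 4.5.1:
- Date and time: gives the result above.
- Date only, strictly before: rejects every Visit 2 sample taken on the day of first dose, for all patients. This can hardly be intended.
- Visit label (the Visit 2 value is the baseline): keeps the sample, but SAP 4.5.1 does not state this as the rule.

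**Size.** The documents give no count. Taking 1–5% of patients as an assumption:
- All 384 patients: 0.01 × 384 = 3.84 and 0.05 × 384 = 19.2, so about 4 to 19 patients.
- 5 mg arm of 32: 0.01 × 32 = 0.32 and 0.05 × 32 = 1.6, so about 0.3 to 1.6 expected patients.

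**The case against.** The strongest objection is that nobody would program it this way. SAP 4.5.1 identifies baseline with Visit 2, Week 0, and leaves that visit only when its value is missing. Here the value exists, and Table 9–1 labels it pre-dose. The protocol asks for exact times of PK samples and drug intake but states no such requirement for the safety draw, so a clock-time comparison is not shown to be planned. This part stands: the loss is conditional on a date-and-time derivation. It does not remove the point, because the operative definition is still expressed relative to first administration, and SAP 4.3 imputes a time as well as a date. The data review in SAP 4.6 and the discretion in SAP 4.3 allow a correction, but neither says what it would be.

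The second objection is rarity. The first dose is taken at the site, and a footnote to Table 9–1 obliges the investigator to record its exact time, on which the same-visit PK window depends. The replacement of an early record applies only when it cannot be clarified. SAP 4.3 also does not say what happens when the date is known and only the time is missing, so such cases should not simply be added to the count. This stands too, and it keeps the expected number low.

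A reader might go further and infer that laboratory baselines are certain to be lost, that the rule spoils sound data in every case it touches, or that a noticeable share of the small 5 mg arm is at risk. The documents do not support this. The loss depends on the reading of SAP 4.5.1, the early-record branch was already defective before the rule acted, and no frequency is given. One affected patient would be 1/32 = 3.1% of the 5 mg arm, but under the assumed 1–5% the expected number there is only about 0.3–1.6.

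**Conclusion.** The point holds in a conditional form. Read by date and time, SAP 4.3 and 4.5.1 together discard the correctly scheduled pre-dose laboratory baseline of any patient whose first-dose date and time is missing, or is recorded before randomization and cannot be clarified. They could also count an abnormal pre-dose value as treatment-emergent. This runs against the stated purpose of the imputation rules, which is to keep patients in the analyses.

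The severity is minor. The number affected is unknown and probably small; the range of 4–19 patients rests wholly on the assumed 1–5%. The safety analyses are descriptive without formal tests (SAP 6.3), and the primary analysis is unaffected. The point is still worth correcting: the rule was written for exactly these patients, and the study's objective includes characterizing safety across doses.

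**What to change.** Add to SAP 4.5.1: whenever the first-dose date and time is imputed or replaced under SAP 4.3, Visit 2 safety samples designated pre-dose in Table 9–1 of the protocol count as taken before first dose and serve as safety baseline, and they are not counted as post-baseline or treatment-emergent.

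Setting the imputed dose to the later of randomization and the last pre-dose sample would not be enough on its own. Dose and sample would then share the same time, and a tied sample is still not before the first dose.

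The cost is one sentence in the SAP and a small change to the baseline and treatment-phase programming. No data collection or primary analysis changes.

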4.4 Interim Analyses and Data Monitoring

A formal interim analysis is not planned. Periodic data review by a DMC will be performed to monitor safety and tolerability. An Independent Data Monitoring Committee (IDMC) will be applied to this study. An external statistical analysis center will provide results to the DMC

4.5 Data Rules

Generally, for each date stored in database a set of organizational variables will be derived in order to describe the temporal context of that date in the specific study: Phase of treatment (pre, during or post study treatment), day relative to the start of study treatment, day relative to the end of study treatment will be provided.

4.5.1 Baseline and Change from Baseline

For efficacy endpoints, the efficacy baseline is defined as the last available value prior to or on the date of randomization. Safety baseline is defined as the last available value before the first study medication administration. If values are missing at the baseline (visit 2, week 0), data recorded at run-in (Visit 1) will be considered as safety baseline value. If run-in record is also missing, the baseline value will be left as missing.

Change from baseline for vital signs or laboratory parameters will in general be displayed as the difference to baseline defined as:

$$\text{Change} = \text{Post baseline value} - \text{baseline value.}$$

In addition, for some parameters the relative change will be analyzed defined as

$$\text{Relative change} = 100\% * [(\text{post baseline value} - \text{baseline value}) / \text{baseline value}].$$

4.5.2 Repeated Measurements

At all visits post-randomization and if not stated otherwise, only the values at scheduled time points will be used for analysis, although unscheduled results will be included in tables reporting any abnormalities, e.g. incidences of high laboratory abnormalities.

For the derived visit “Any time post baseline” this will include any measurement after initiation of study drug, including unscheduled assessments.

4.5.3 Laboratory Data Handling

The data of hematology, clinical chemistry, and coagulation will be provided by central laboratories. Additional re-tests for liver monitoring will be done locally.

For values which are below the lower limit of quantification (LLOQ), half the value of the LLOQ will be used for analysis. Differences between two values of below the LLOQ will be assigned values of 0.

In case of measurements above the upper limit of quantification (ULOQ), the following rules will be applied:

- The ULOQ will be used for calculations.
- Corresponding tables and figures will get a footnote indicating that “Values above the upper limit of quantification of ULOQ were replaced by ULOQ.”
- Tables displaying maximum values will show up “>ULOQ” as maximum.

If more than one assessment occurred at any post-baseline visit (repeated measures at same visit), the last valid (non-missing) value will be used in the summaries. Unscheduled laboratory data will be listed and included in the summary tables.

4.5.4 Subgroup analyses

In order to assess the homogeneity of the dose response across the most important prognostic and predictive factors, subgroup analyses will be performed.

‘Key’ subgroups include:

- LVEF(%) at baseline: ≤ 25 vs. > 25
- LVEF(%) at baseline: ≤ 40 vs. > 40
- LVEF(%) at baseline: ≤ 45 vs. > 45
- NT-proBNP (pg/ml) at baseline: \leq median vs. $>$ median
- NYHA class at baseline: II vs. III / IV
- Prior β -blocker: yes vs. no

All other exploratory subgroups comprise demographic and baseline characteristics specified in section 6.1.2.

If the total number of subjects in a subgroup category is too small, the respective subgroup category will be either omitted from the analysis or combined with other categories, if a logical combination to another subgroup category is possible.

Prior hospitalization for heart failure is defined based on one of inclusion criterions.

CRF item (subject group) selected	Prior hospitalization (outpatients visit)
CHF Hospitalization/ unscheduled outpatient clinic visit with BNP/NTproBNP measurement in the last 3 months	Yes
Only BNP/NTproBNP measurement in the last 4 weeks	No
Combination of CHF Hospitalization/ unscheduled outpatient clinic visit with BNP/NTproBNP measurement in the last 3 months and additional measurement in the last 4 weeks	Yes

4.6 Blind Review

The results of the final data assessment will be documented in the final list of important deviations, validity findings and assignment to analysis set(s). Any changes to the statistical analysis prompted by the results of the review of study data will be documented in an amendment and, if applicable, in a supplement to this SAP.

5. Analysis Sets

Documentation of protocol deviations and assignment of patients to analysis sets will be performed according to the sponsor’s applicable Standard Operating Procedures and ocor Operation Instructions.

5.1 Assignment of analysis sets

Final decisions regarding the assignment of subjects to analysis sets will be made during the review of study data and documented in the final list of important deviations, validity findings and assignment to analysis set(s) (see section 4.6).

Data for all patients who signed informed consent but were not randomized will not be included in any statistical analyses except standard disposition tables and listings provided in the clinical study report (Screening failures and discontinued patients).

The statistical analysis sets are defined as follows:

Full analysis set (FAS)

The FAS population consists of all randomized unique patients. According to the ICH E9 guideline, this analysis set is as complete as possible and as close as possible to the intent-to-treat (ITT) ideal. Patients will be analyzed as randomized. The FAS will be used to display baseline characteristics and to display efficacy analyses. Sensitivity analyses are based on the FAS population. For the analyses conducted in FAS, patients will be analyzed as randomized per IxRs.

Safety analysis set (SAF)

The SAF population consists of all randomized patients who received at least one dose of study medication after randomization. The SAF will be used to display safety analyses. For analyses conducted in SAF, patients will be analyzed as treated.

Per-protocol set (PPS)

The protocol defines a PPS. Since there are two primary efficacy variables, we will define PPS LVEF and PPS BNP, specific to the presence of non-missing data for each variable separately.

Per-protocol set for LVEF (PPS LVEF): The PPS LVEF population consists of all FAS population patients without validity findings. Validity findings may include adherence and compliance issues and the violation of inclusion / exclusion criteria affecting efficacy evaluation. If the left ventricular ejection fraction of this subject is measured after first dose of study medication but within a specified time frame this subject will not be excluded from PPS LVEF. The patients with invalid/missing baseline value or missing post-baseline value not due to CV death or HF hospitalization will be excluded from the PPS LVEF. The primary analysis of LVEF will be conducted in PPS LVEF.

Per-Protocol set for NT-proBNP (PPS BNP): The PPS BNP population consists of all FAS population patients without validity findings. Validity findings may include adherence and compliance issues and the violation of inclusion / exclusion criteria affecting efficacy evaluation. If the NT-proBNP (pg/mL) of this subject is measured after first dose of study medication but within a specified time frame this subject will not be excluded from PPS BNP. The patients with invalid/missing baseline value or missing post-baseline value not due to CV death or HF hospitalization will be excluded from the PPS BNP. The primary analysis of NT-proBNP will be conducted in PPS BNP.

A list of potential validity findings will be provided in a separate important deviations and validity specifications document which will be finalized before database lock. The detailed definitions and the assignment of patients to this analysis set will be based on the validity review meeting. Patients will be analyzed as treated.

Pharmacokinetic analysis set (PKS)

The PKS population consists of all patients treated with neladenoson bialanate with at least 1 valid BAY 84-3174 plasma concentration and without protocol deviation that would interfere with the evaluation of the PK data.

6. Statistical Methodology

The formal statistical analyses will be both descriptive and inferential. Summaries will be provided for each of the treatment group. All of analyses planned in this SAP will be repeated in Japanese subjects only.

